A Randomized Parallel-Group Study to Evaluate the Efficacy and Tolerability of Two Dosing Regimens of CTP-543 in Adult Patients with Moderate to Severe Alopecia Areata

[figure not shown]
CP543.2002, Protocol Amendment #1 03 January 2019

The main purpose of this amendment #1 (to original protocol dated 17 December 2018), is to modify the Schedule of Assessments. It was noted that an ECG at Screening had not been checked in the table. An 'X' has been subsequently added to the Schedule of Assessments for the Screening visit. The Schedule of Assessments was the only section updated to reflect this change.

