Patients will provide informed consent prior to completing any screening procedures. Patients meeting screening criteria will continue to the Day 1 Randomization Visit for review of eligibility and baseline assessments, including SALT assessment, physical examination, clinical laboratory assessments, vital signs, and electrocardiogram. Patients meeting all eligibility criteria will be randomized to 1 of 2 CTP-543 treatment arms. Randomization will be stratified by classification of alopecia areata subtype into one of the following three categories: 1) alopecia areata, 2) alopecia totalis or alopecia universalis, or 3) alopecia ophiasis.

Patients will take the first dose of study drug in the clinic on Day 1. Patients will be instructed to take study drug every 12 hours. Patients should dose study drug in the clinic on all Study Visit Days after clinical laboratory blood draws are completed.

Patient safety will be monitored throughout the trial. During the first 8 weeks of the Treatment Period, hematology will be conducted every 2 weeks, followed by an assessment every 4 weeks thereafter through completion of the study at 24 weeks. Lipid levels will be assessed every 12 weeks throughout the Treatment Period. Significant cytopenias or other hematologic abnormalities will be managed by severity through dose interruption, or discontinuation, and signs and symptoms of infection will be closely monitored and treated promptly. Patients who experience intolerable symptoms during treatment may discontinue the study at the discretion of the Investigator. Patients may withdraw consent at any time.

The Treatment Period will last 24 weeks to assess CTP-543 dosed BID vs CTP-543 dosed QD. Assessment of treatment response with SALT for efficacy will occur at 4, 8, 12, 16, 20 and 24 weeks. Upon completion of the 24-week Treatment Period, patients will be eligible to either complete treatment and exit the study following the safety follow-up visit, or roll-over into a long-term open-label extension study.

Number of patients (planned):

Approximately 60 patients are planned to be enrolled in the study; approximately 30 patients per treatment arm.

Diagnosis and main criteria for inclusion:

Patients eligible for enrollment in the study must meet all of the following inclusion criteria and none of the exclusion criteria.

Inclusion Criteria:

1. Written informed consent, and authorization for release and use of protected health information.

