2. Between 18 and 65 years of age, inclusive, at the time of informed consent.
3. Definitive diagnosis of alopecia areata. Totalis or universalis and ophiasis subtypes must have a current episode lasting at least 6 months and not exceeding 10 years at the time of Screening. Total disease duration greater than 10 years is permitted.
4. At least 50% scalp hair loss, as defined by a SALT score ≥ 50 , at Screening and Baseline.
5. If of reproductive age, willing and able to use a medically highly effective form of birth control during the study and for 30 days following last dose of study medication. Examples of medically highly effective forms of birth control are:
 - a. Surgical sterility (via vasectomy, hysterectomy or bilateral ligation) or post-menopausal females
 - b. Sexual partner is sterile, or of the same sex
 - c. Implants of levonorgestrel in females
 - d. Oral contraceptive (combined or progesterone only) in females
 - e. Double-barrier method (any combination of physical and chemical methods)
 - f. Intrauterine device in females, or other method with published data showing that the lowest expected failure rate is less than 1% per year
6. Willing to comply with the study visits and requirements of the study protocol.

Exclusion Criteria:

1. History or presence of hair transplants.
2. Treatment with other medications or agents within 1 month of Screening or during the study that may affect hair regrowth or immune response, including but not limited to: corticosteroids administered orally, by injection, or applied to areas of skin affected by alopecia; platelet-rich plasma injections; topical application to affected areas of anthralin, squaric acid, diphenylcyclopropenone, or minoxidil.
3. Treatment with systemic immunosuppressive medications including but not limited to methotrexate, cyclosporine, and azathioprine; chloroquine derivatives; Janus kinase inhibitors (ruxolitinib, tofacitinib, etc) or etanercept within 3 months of Screening or during the study; or biologics (adalimumab, atlizumab, canakinumab, certolizumab, fontolizumab, golimumab, infliximab, mepolizumab, rituximab, secukinumab, tocilizumab, ustekinumab) within 6 months of Screening or during the study.

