4. Active scalp inflammation, psoriasis, or seborrheic dermatitis requiring topical treatment to the scalp, significant trauma to the scalp, or other scalp condition that may interfere with the SALT assessment, or untreated actinic keratosis anywhere on the body at Screening and/or Baseline.
5. Known history of moderate to severe androgenic alopecia or female pattern hair loss prior to alopecia areata.
6. Unwilling to maintain a consistent hair style, including shampoo and hair products (including hair dye, process, and timing to hair appointments), and to refrain from weaves or extensions

throughout the course of the study, or shaving of scalp hair for 2 weeks preceding a SALT assessment.

7. Use of adhesive wigs, other than banded perimeter wigs, during the study.
8. History of a lymphoproliferative disease or malignancy, other than non-melanoma skin cancer or cervical carcinoma. Patients with 3 or more basal or squamous cell carcinomas diagnosed in the past 2 years are excluded.
9. Atypical nevi or cutaneous lesions that are suspicious for malignancy.
10. History of solid organ or hematological transplantation.
11. Systemic or invasive infection, as evidenced by fever, inflammation, or systemic signs of illness (e.g., malaise, myalgia, specific symptoms like pain, shortness of breath) within 2 weeks prior to first dose of study drug.
12. Abnormal levels of thyroid stimulating hormone at Screening, defined as $<0.9 \times$ the lower limit of normal (LLN) and $>1.2 \times$ the upper limit of normal (ULN).
13. Screening labs outside the normal range for parameters associated with potential risk for treatment under investigation. This will include but is not limited to:
 - a. Platelets $\leq 120 \times 10^9/L$ or $\geq 600 \times 10^9/L$
 - b. Absolute neutrophil count $\leq 1.5 \times 10^9/L$
 - c. Hemoglobin levels $\leq 11 \text{ g/dL}$ for females, or hemoglobin levels $\leq 12.5 \text{ g/dL}$ for males
14. Screening blood glucose levels of hemoglobin A1c $\geq 6.5\%$ (48 mmol/mol).
15. Abnormal liver function at Screening, defined as $\geq 1.5 \times$ ULN of serum alanine transaminase, serum aspartate transaminase, serum alkaline phosphatase, or total bilirubin (unless isolated Gilbert's syndrome).
16. Abnormal renal function (estimated glomerular filtration rate $<60 \text{ mL/min/1.73 m}^2$ using the MDRD equation) at Screening.

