7.2. Patient Exclusion Criteria

1. History or presence of hair transplants.
2. Treatment with other medications within 1 month of Screening or during the study that may affect hair regrowth or immunosuppression, such as: corticosteroids administered orally, by injection, or applied to areas of skin affected by alopecia; topical application of anthralin, squaric acid, diphenylcyclopropenone, or minoxidil.
3. Treatment with systemic immunosuppressive medications including but not limited to methotrexate, cyclosporine, and azathioprine; chloroquine derivatives; JAK inhibitors within 3 months of Screening (ruxolitinib, tofacitinib, etc), etanercept; or biologics (adalimumab, atlizumab, canakinumab, certolizumab, fontolizumab, golimumab, infliximab, mepolizumab, rituximab, secukinumab, tocilizumab, ustekinumab) within 6 months of Screening.
4. Active scalp inflammation, psoriasis, or seborrheic dermatitis requiring topical treatment to the scalp, significant trauma to the scalp, or untreated actinic keratosis on the scalp at Screening and/or Baseline.

5. Known history of moderate to severe androgenic alopecia or pattern hair loss prior to alopecia areata.
6. Unwilling to maintain a consistent hair style, including shampoo and hair products (including hair dye, process, and timing to visits), and to refrain from weaves or extensions throughout the course of the study, or shaving of scalp hair for at least 2 weeks prior to a SALT assessment.
7. Use of adhesive wigs, other than banded perimeter wigs, during the study.
8. History of a lymphoproliferative disease or malignancy with recurrence within the 5 years prior to the first study drug administration, other than non-melanoma skin cancer or cervical carcinoma. Patients with 3 or more basal or squamous cell carcinomas diagnosed in the past 2 years are excluded.
9. Atypical nevi or cutaneous lesions that are undiagnosed but suspicious for malignancy.
10. History of solid organ or hematological transplantation.
11. Systemic or invasive infection, as evidenced by fever, inflammation, or systemic signs of illness (e.g., malaise, myalgia, specific symptoms like pain, shortness of breath) within 2 weeks prior to first dose of study drug.
12. Abnormal levels of thyroid stimulating hormone at Screening, defined as $<0.9 \times$ the lower limit of normal (LLN) and $>1.2 \times$ the upper limit of normal (ULN).

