13. Screening labs outside the normal range for parameters associated with potential risk for treatment under investigation. This will include but is not limited to:
 - a. Platelets $\leq 120 \times 10^9/L$ or $\geq 600 \times 10^9/L$
 - b. Absolute neutrophil count $\leq 1.5 \times 10^9/L$
 - c. Hemoglobin levels $\leq 11 \text{ g/dL}$ for females, or hemoglobin levels $\leq 12.5 \text{ g/dL}$ for males
14. Screening blood glucose levels of hemoglobin A1c $\geq 6.5\%$ (48 mmol/mol).
15. Abnormal liver function at Screening, defined as $\geq 2 \times$ ULN of any 3 or more of the following: serum alanine transaminase, serum aspartate transaminase, serum alkaline phosphatase, total bilirubin.
16. Abnormal renal function (estimated glomerular filtration rate $<60 \text{ mL/min}/1.73 \text{ m}^2$ using the MDRD equation).
17. At screening, any active or previous Hepatitis B or C infection, or known human immunodeficiency virus infection.
18. Vaccination with herpes zoster vaccine or any live virus vaccine within 6 weeks prior to Screening or during the study.
19. Positive TB test, or history of incompletely treated or untreated tuberculosis.

NOTE: In cases where performance of a QuantiFERON-TB Gold test is not possible, testing with a Tuberculin Skin Test (TST) may be an option after consultation with the Medical Monitor. If the TST is negative, patients can be randomized into the study, assuming they meet all other inclusion and none of the exclusion criteria. If results are

equivocal, or there is reason to believe the result is a false positive, a QuantiFERON-TB Gold must be performed before a subject is eligible for randomization.

20. Prolonged QT or heart-rate corrected QT (QTc) interval with Fridericia's correction (QTcF) > 450 msec for males or QTcF > 470 msec for females.
21. History of alcohol, medication, or illicit drug abuse within 1 year before the first dose of study drug.
22. Females who are nursing, pregnant, or planning to become pregnant while in the study, and for 30 days after last dose of study medication.
23. Participation in another investigational study within the greater of 4 weeks or 5 half-lives of an investigational medication prior to screening or during the study.

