### **2.3 Study Population**

The study population will consist of male and female patients of any ethnicity between 18 and 65 years of age, inclusive, with diagnosis of alopecia areata with a current episode lasting at least 6 months and not exceeding 10 years at the time of Screening. Total disease duration greater than 10 years is permitted. Patients must also exhibit at least 50% scalp hair loss, as defined by a SALT  $\geq 50$ , at Screening and Baseline.

A full list of the inclusion and exclusion criteria can be found in Sections 7.1 and 7.2 in the CP543.2002 Protocol.

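### The Synopsis and Section 7.2 print different liver and malignancy exclusions, and the protocol does not say which governs

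*Protocol*

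**What the plan says.** The protocol prints its numbered exclusions twice, in the Synopsis and in Section 7.2. The Synopsis list and Section 7 open with the same rule: patients "must meet all of the following inclusion criteria and none of the exclusion criteria". Of Amendment 1 the protocol says: "The Schedule of Assessments was the only section updated to reflect this change". Both lists are therefore current text.

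**Liver, no. 15.** The Synopsis excludes at or above 1.5 × "ULN of serum alanine transaminase, serum aspartate transaminase, serum alkaline phosphatase, or total bilirubin", with an exemption for isolated Gilbert's syndrome. Section 7.2 excludes at or above 2 × "ULN of any 3 or more of the following: serum alanine transaminase, serum aspartate transaminase, serum alkaline phosphatase, total bilirubin", with no exemption.

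**Malignancy, no. 8.** The Synopsis wording is "History of a lymphoproliferative disease or malignancy, other than non-melanoma skin cancer or cervical carcinoma". Section 7.2 has "History of a lymphoproliferative disease or malignancy with recurrence within the 5 years prior to the first study drug administration", followed by the same skin and cervical exceptions.

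Neither document ranks the lists. The nearest thing is SAP 2.3: "A full list of the inclusion and exclusion criteria can be found in Sections 7.1 and 7.2 in the CP543.2002 Protocol".

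**The concern.** Liver function and cancer history are entry gates for a drug whose potential to suppress immunity the protocol itself raises in Section 9.1, where it tells investigators to probe cancer risk. Here each gate has two definitions. About 10 sites could in good faith apply different ones, and a site working only from Section 7.2, the section devoted to selection, would apply the looser rule on both items. The same patient could also be a protocol deviation under one list and not under the other when deviations are classified under SAP 5.2. What is at stake is patient safety at entry and consistent conduct, not the efficacy estimate.

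**Working it through.** There is no planned figure to reproduce. The check applies each printed rule to the same patients.

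**Liver, no. 15.** Inputs are ALT, AST, ALP and total bilirubin as multiples of ULN, Gilbert's syndrome aside.

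- Synopsis rule: exclude if the number of tests ≥ 1.5 is at least 1.
- Section 7.2 rule: exclude if the number of tests ≥ 2 is at least 3.

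| ALT, AST, ALP, bilirubin | Tests ≥ 1.5 | Tests ≥ 2 | Synopsis no. 15 | Section 7.2 no. 15 |
|---|---|---|---|---|
| 3, 1, 1, 1 | 1 | 1 | excluded | not excluded |
| 5, 5, 1, 1 | 2 | 2 | excluded | not excluded |
| 1.6, 1, 1, 1 | 1 | 0 | excluded | not excluded |
| 2, 2, 2, 1 | 3 | 3 | excluded | excluded |

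With ALP and bilirubin normal, at most two tests can be raised, so no ALT and AST values can meet Section 7.2 no. 15. In the other direction, three tests at ≥ 2 × ULN include at least two that are not bilirubin, and both exceed 1.5 × ULN. Anyone excluded by the Section 7.2 rule is therefore also excluded by the Synopsis rule, which is the tighter of the two.

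**Malignancy, no. 8.** Take a solid tumour, not skin or cervical, treated six years before the first dose and never recurrent. The Synopsis has no time limit, so the patient is excluded. Section 7.2 requires recurrence within five years, so the patient is not. At six years the example lies outside the window however recurrence is read. For lymphoproliferative disease it is unclear whether the recurrence condition applies, so nothing is claimed there.

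**Other items.** Neither list is stricter throughout:

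- No. 2: the Synopsis names "platelet-rich plasma injections; topical application to affected areas of anthralin" and other topical agents. Section 7.2 does not name platelet-rich plasma, although its list is open-ended, and it does not confine topical use to affected areas.
- No. 3: the Synopsis gives a three-month window for immunosuppressants, JAK inhibitors and etanercept. Section 7.2 attaches three months to JAK inhibitors and leaves the window for methotrexate, cyclosporine, azathioprine and etanercept unclear.
- No. 4: untreated actinic keratosis counts at any body site in the Synopsis and only on the scalp in Section 7.2. The Synopsis alone adds other scalp conditions that could disturb SALT scoring.
- No. 9: Section 7.2 limits suspicious lesions to undiagnosed ones.
- No. 16: only the Synopsis ties the renal criterion to Screening.
- No. 20: only the Synopsis names a history of prolonged QT syndrome, but it limits the QTcF threshold to the Screening value. Section 7.2 does not. Table 1 schedules a Day 1 ECG, and Section 6.4 places it in the visit that reviews eligibility. A man with QTcF 440 msec at Screening and 460 msec on Day 1 passes the Synopsis limit of 450 and fails the Section 7.2 limit of 450.
- Nos. 24 and 25: Section 7.2 omits the Synopsis restriction to systemic dosing, so it is the stricter text.

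**The case against.** The strongest reply is that nothing here is a true contradiction. Both lists are exclusions under the same opening rule, so a patient barred by either is barred, and no patient must break one list to satisfy the other. That is right as logic, and it lowers the severity. It does not remove the problem, because no text tells sites to read the lists together.

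A second reply is that other provisions catch these patients. Exclusion 13 is open-ended on screening laboratory values and exclusion 27 allows exclusion on risk-benefit grounds; both are in both lists. Section 9.9 makes the investigator assess Screening results for eligibility, and serum chemistry is repeated every 2 weeks for 8 weeks and every 4 weeks after that. These narrow the gap. But exclusions 13 and 27 give no liver or malignancy limit, and the repeat chemistry acts only after dosing has begun.

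Some stronger readings are tempting and are not supported:

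- A reader might infer that Section 7.2 would admit a patient with any ALT and AST values. That is true of no. 15 alone; exclusions 13 and 27 still allow the investigator to refuse.
- A reader might take SAP 2.3 to make Section 7.2 govern. It says where a full list is found and does not say that this list overrides the Synopsis.
- A reader might infer that the Synopsis is the safe default. Nos. 20, 24 and 25 show otherwise.
- A reader might want a count of conflicting items. Which wording differences are substantive is a matter of judgement, so none is given.

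**Conclusion.** The inconsistency is real for at least nos. 15 and 8, and it rests on the printed text alone. It should be fixed, as an internal inconsistency in safety entry criteria, but it does not undermine the trial's results. Eligibility is settled before the 1:1 randomization, so whichever list a site uses applies to both regimens alike; a reader who inferred bias in the SALT comparison would go beyond the documents. How many of the roughly 60 patients would be affected depends on the distribution of screening values and histories, which the documents do not give.

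**What to change.** By amendment, print one reconciled list in Section 7 and have the Synopsis cross-refer to it, using the Synopsis text for nos. 8 and 15.

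Section 12.4 makes sites wait for IRB approval of a non-administrative amendment. Until then, send a site notice that a patient who meets an exclusion in either list is not eligible. This waives neither list and needs no item-by-item choice of text. For no. 20 it means exclusion for a history of prolonged QT syndrome, or for QTcF above 450 msec (males) or 470 msec (females) at Screening or on the Day 1 ECG before randomization. Unclear cases under no. 3 should go to the Medical Monitor before randomization.

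The cost is one amendment, one site notice and possibly a few more screen failures. Design, endpoints and sample size do not change.

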7.3. Patient Withdrawal Criteria

All patients are free to withdraw from participation in the study at any time, for any reason, and without prejudice. The Investigator must withdraw any patient from the study if the patient requests to stop participating in the study. The Investigator, Sponsor, or its designee may remove a patient from the study at any time and for any reason. In addition, patients should be withdrawn if they:

- Experience an intolerable adverse event
- Require a medication that is prohibited by the protocol
- Do not follow guidelines specified in the protocol (ie, is noncompliant with protocol procedures or study treatment administration)
- Any medically appropriate reason or significant protocol violation, in the opinion of the Investigator
- Are lost to follow up

Patients who withdraw or are withdrawn from the study will not be replaced.

7.3.1. Patient Withdrawal Procedures

A patient who prematurely discontinues study treatment/study participation should have all Week 24 assessments performed as an Early Termination Visit, and return for the Safety Follow-up Visit (See [Table 3](#)). The Safety Follow-Up Visit may be waived by the Sponsor in instances where patients have discontinued dosing prior to the Early Termination Visit on a case-by-case basis.

If a patient terminates early from the study, the Investigator will record the reason(s) for early termination on the relevant electronic case report form (eCRF). The specific reason for the withdrawal should be carefully documented on the eCRF.

Patients who require a dose interruption lasting more than 21 consecutive days for management of adverse events should be discontinued from the study. Adverse events resulting in patient early termination will be followed to the satisfactory resolution and determination of outcome, as ascertained by the Investigator (and/or Sponsor, or its designee); See Section [10](#) Adverse Events. The data will be recorded on the appropriate eCRF.

7.4. Criteria for Study Termination

There are no prospective stopping criteria for this study. The Sponsor reserves the right to discontinue the study at any time for clinical or administrative reasons.

Any termination required by the Sponsor must be implemented by the Investigator, if instructed to do so, in a time frame that is compatible with the patient's well-being.

8. DESCRIPTION OF STUDY TREATMENTS

8.1. Description of Treatments

In the Treatment Period, patients will be stratified by alopecia areata subtype and randomized to 1 of 2 CTP-543 treatment arms in a 1:1 ratio. Treatments arms will include:

- CTP-543 8 mg BID (every 12 hours)
- CTP-543 16 mg QD (16 mg in the morning and placebo tablet in the evenings)

8.2. Safety Criteria and Management for Stopping Doses

Patients who experience hematologic adverse events as described in [Table 3](#) or adverse events that may reflect an unfavorable risk-benefit profile may have their dose interrupted or be discontinued from the study at the discretion of the Investigator. The Medical Monitor should be consulted whenever possible prior to decisions for dose interruption or patient discontinuation from the study.

Patients who require a dose interruption lasting more than 21 consecutive days will be discontinued from the study.

Patients who are discontinued from the study should undergo an Early Termination Visit and subsequent Safety Follow-up Visit as appropriate per [Section 7.3.1 Patient Withdrawal Procedures](#), and associated adverse events followed as described in [See Section 10 Adverse Events](#).

Hematology and serum chemistry parameters will be assessed every 2 weeks for the first 8 weeks of the Treatment, and every 4 weeks thereafter for the remainder of the study. Prior to dose interruption, hematology parameters should be confirmed with repeat testing at an interval deemed appropriate by the Investigator (e.g., at the next protocol-defined visit or an Unscheduled Visit), except in severe cases where immediate interruption of dosing is necessary for the safety of the patient. **Blood draws confirming dose interruption criteria should occur prior to the first daily dose on the day of draw.**

Dose interruption requirements for hematologic abnormalities are provided below. However, less significant changes may warrant clinical intervention and the Investigator should use his/her best clinical judgment when considering a dose interruption whether for singular or aggregate hematology results above the limits provided in [Table 3](#), or for other clinical signs, symptoms, or considerations that suggest dose interruption is in the best interest of the patient.

Table 3: Selected Hematologic Thresholds for Dose Interruption

Neutrophil Count	Dose Adjustment
Less than $1 \times 10^9/L$	Interrupt dose until recovered to greater than $1.5 \times 10^9/L$ and resume dosing at previous dose
Female Hemoglobin Level	Dose Adjustment
Less than 10 g/dL	Interrupt dose until recovered to greater than 11.5 g/dL and resume dosing at previous dose
Male Hemoglobin Level	Dose Adjustment
Less than 11.5 g/dL	Interrupt dose until recovered to greater than 13 g/dL and resume dosing at previous dose
Platelet Count	Dose Adjustment
Less than $75 \times 10^9/L$	Interrupt dose until recovered to greater than $75 \times 10^9/L$ and resume dosing at previous dose
Greater than $750 \times 10^9/L$	Interrupt dose until recovered to less than $600 \times 10^9/L$ and resume dosing at previous dose

Upon dose interruption, the parameters that triggered the interruption should be monitored at least weekly until either: 1) recovery above the threshold for dosing resumption is achieved, or 2) the allowable 21-day interruption has elapsed. In the case of severe neutropenia (neutrophil counts less than $0.5 \times 10^9/L$) patients should discontinue the study drug and receive instructions to seek medical help if they develop fever or signs of infection. Patients who discontinue the study due to lack of acceptable recovery of parameters within 21 consecutive day dose interruption period should continue to be monitored as appropriate through acceptable clinical resolution.

If the patient recovers above the threshold for interruption before the 21 consecutive day interruption period ends, they may remain in the study. Subsequent dose interruptions within a patient should be discussed with the Medical Monitor to determine continued participation in the study.

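### Protocol 8.2 makes a Table 3 dose interruption discretionary in one paragraph and required in another, and the neutrophil row is not tied to the separate instruction for counts below 0.5 x 10^9/L

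*Protocol*

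**What the plan says.** All the relevant text is in Protocol Section 8.2.

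- **Opening sentence.** It covers "Patients who experience hematologic adverse events as described in" Table 3, together with other adverse events that suggest an unfavorable balance of risk and benefit. These patients "may have their dose interrupted or be discontinued from the study at the discretion of the Investigator". The Medical Monitor is to be consulted where possible.
- **Paragraph introducing Table 3.** "Dose interruption requirements for hematologic abnormalities are provided below". It then says that "less significant changes may warrant clinical intervention and the Investigator should use his/her best clinical judgment when considering a dose interruption", and extends that judgment to other clinical signs and considerations.
- **Table 3, neutrophil row.** The trigger is a count below 1 x 10^9/L, with no lower bound. The action is "Interrupt dose until recovered to greater than $1.5 \times 10^9/L$ and resume dosing at previous dose".
- **Text after Table 3.** For severe neutropenia, defined as a count below 0.5 x 10^9/L, "patients should discontinue the study drug and receive instructions to seek medical help if they develop fever or signs of infection". No resumption step follows.

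The design descriptions (Protocol Synopsis and Section 6.3, SAP 2.2) add only that hematologic abnormalities are handled according to severity by interruption or discontinuation. They give no cut-points.

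**The concern.** A site that obtains a result beyond a Table 3 limit needs to know whether it must act. The opening sentence suggests a choice, whereas the later paragraph and the rows suggest none. For a neutrophil count below 0.5 x 10^9/L, the site also needs to know whether stopping is temporary.

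The main stake is patient safety. Section 9.1 refers to the drug's potential immunosuppressive properties, Section 7.4 sets no prospective study stopping criteria, and SAP 11 plans no data monitoring committee. The patient-level rule in 8.2 therefore carries much of the hematologic protection.

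The second stake is the tolerability summary. SAP 9.2 tabulates, by regimen, adverse events leading to interruption and those leading to discontinuation. If sites read 8.2 differently, those counts depend partly on the site's reading. A patient taken off drug instead of resumed may also have SALT carried forward under SAP 8.4.1.

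**Working it through.** No sample size, error rate or other planned figure is involved, so the check is to apply each instruction to the same blood count. Counts are in 10^9/L.

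**Inputs (all Protocol 8.2):** row trigger below 1; row resumption above 1.5; severe neutropenia below 0.5; longest allowed interruption 21 consecutive days.

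| Count | Opening sentence | Introductory paragraph and Table 3 row | Sentence after Table 3 |
|---|---|---|---|
| 0.8 (below 1, not below 0.5) | Interruption or discontinuation at discretion | Interruption required; resume above 1.5 | Does not apply |
| 0.4 (below 1 and below 0.5) | Interruption or discontinuation at discretion | Interruption required; resume above 1.5 | Discontinue study drug; no resumption step |

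**Step 1, status of the rule.** At 0.8 only the first two instructions apply, and they disagree on whether the Investigator has a choice. The later paragraph does leave room for judgment, but for results short of the limits and for other clinical considerations, not for whether a crossed limit counts. The same disagreement affects all five Table 3 rows, since the opening sentence refers to the table as a whole.

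**Step 2, overlap below 0.5.** Any count below 0.5 is also below 1, so every severe neutropenia meets the row's trigger. Suppose 0.4 recovers to 1.6 within 21 days. Since 1.6 is above 1.5, the row returns the patient to the previous dose. The sentence after the table does not. The two agree on stopping and part only on restarting.

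**Step 3, does another passage settle it?** Table 3 has no footnote or exception for counts below 0.5, and the sentence does not say that it replaces the row. The general statement about handling by severity fits a tiered rule but supplies no limits. Medical Monitor consultation may reduce differences in practice but does not fix the written rule.

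**Step 4, reach.** Exclusion criterion 13c in Section 7.2 admits men with hemoglobin just above 12.5 g/dL and women just above 11 g/dL. The Table 3 triggers are below 11.5 and below 10 g/dL. The differences are 12.5 - 11.5 = 1.0 and 11 - 10 = 1.0 g/dL, so for patients who enter near the limit a fall of little more than 1 g/dL is enough. Step 1 is thus not confined to extreme events. This shows who could be affected, not how many.

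**The case against.** **The opening sentence may be about which action, not whether to act.** It spans two groups of events and two actions, so its discretion could mean the choice between interruption and discontinuation. The operative text is then uniformly imperative. This reading is possible, but the protocol does not state it. The same permissive verb also governs the other adverse events, where it plainly leaves the Investigator free to do neither.

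**The sentence on counts below 0.5 is an ordinary exception.** It directly follows the table, names a narrower range and fits handling by severity. The table's title speaks only of interruption thresholds. The protocol also generally uses interruption for temporary stops and discontinuation for ending treatment (for example Sections 7.3.1 and 10.2.5). Most of this stands. It is the most natural reading, which is why the overlap is the lesser part of the point. What remains is that neither the row nor the sentence says so.

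**A reader might infer opposite instructions, or that a patient at 0.4 could simply stay on drug.** The documents do not support either. Both instructions stop dosing at once, and continuing would mean setting aside both the row and the sentence.

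**A reader might infer a distorted regimen comparison.** Patients, investigators and site staff are unaware of the regimen (Protocol 6.3), and safety summaries are descriptive without testing (SAP 9.1). No mechanism favoring one regimen is evident. With about 10 sites and stratification by subtype only, differences between sites need not balance exactly across arms, but this is mainly noise.

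**Conclusion.** The point holds as an internal inconsistency in a patient-safety rule. Its firm part is the conflict between discretion and requirement for crossing any Table 3 limit, which no other passage resolves. Its secondary part is a missing link between the neutrophil row and the instruction for counts below 0.5 x 10^9/L, which differ only on whether dosing may resume.

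The size cannot be derived, because the documents give no rate of Table 3 crossings. It is tempting to scale from the three Grade 3 or 4 hematologic changes reported for the earlier study (Protocol 4.4.1). They do not serve: they were spread equally across the dose groups including placebo, the parameters are not named, and nothing maps Table 3 limits to toxicity grades.

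The conclusion assumes only that sites work from the text of 8.2. Site training or the Site Operations Manual may give a single reading, but neither is among the documents. The matter should be corrected because it concerns safety and the correction is cheap, not because a material effect on the results has been shown.

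**What to change.** Reconcile the passages within Section 8.2:

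1. State once whether crossing a Table 3 limit makes interruption mandatory or leaves it to discretion, and use the same status in the opening paragraph, the paragraph introducing the table and the rows.
2. Either give the neutrophil row and the severe neutropenia sentence ranges that do not overlap, or have one expressly refer to the other and say which governs. In the same edit, confirm that discontinuing the study drug there excludes resumption, if that is what is meant.

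Which rule applies is for the sponsor's medical team; no view is taken here. The cost is a short wording amendment and a notice to sites. No change to the sample size, the assessments or the SAP analyses is needed.
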